### **8.2 Handling of Missing Data**

Missing data will be imputed using the following methods for the efficacy analyses:

- **Non-Responder Imputation** incorporating Multiple Imputation (MI) to handle missing data due to CCOVID-19 (NRI-C): the NRI-C analysis will categorize any subject who does not have evaluation during a pre-specified visit window (either due to missing assessment or due to early withdrawal from the study) as a non-responder for that visit. The exceptions are: 1) when the subject is a responder both before and after a specific visit window, in which case the subject will be categorized as a responder for the visit. (Only observations within the same analysis period will be used.) 2) missing data due to COVID-19 infection or logistical restriction will be handled by Multiple Imputation. In addition, all assessments after the start of rescue medications or prohibited medications will not be included in the analyses; as a result, subjects will be counted as non-responders thereafter and will not be imputed by MI. The NRI-C will be the primary approach in the analyses of categorical variables in Period A.

- A sensitivity analysis for categorical endpoints will use NRI with No special data handling for missing due to COVID-19 (NRI-NC). NRI-NC will be performed in the same way as NRI-C without the exception #2 above. That is, missing due to COVID-19 infection or logistical restriction will also be counted as non-responders. Subjects whose change/percent change from Baseline cannot be calculated because of a missing Baseline will be considered as a non-responder at all post-baseline visits in both NRI-C and NRI-NC approaches.
- Mixed-Effect Model Repeat Measurement (MMRM): The repeated measures analysis will be conducted using the mixed-effect model including observed measurements at all visits. The mixed-effect model includes the categorical fixed effects of treatment, visit and treatment-by-visit interaction, main stratification factors at randomization (vIGA-AD categories [moderate vs severe]), and the continuous fixed covariates of baseline measurement. An unstructured variance covariance matrix will be used. Parameter estimation is based on the assumption of data being missing at random and using the method of restrictive maximum likelihood (REML). The fixed effects will be used to report visit means at corresponding visits. MMRM will be the primary approach in the analysis of continuous variables in Period A.
- Observed Cases (OC): The OC analysis will not impute values for missing evaluations, and thus a subject who does not have an evaluation on a scheduled visit will be excluded from the OC analysis for that visit. OC will exclude values after a subject prematurely discontinues from study drug. OC analysis will be used for the summaries of long-term efficacy for all variables in Period B.
- Multiple Imputation (MI): The MI approach will be used as a sensitivity analysis for the primary efficacy endpoint and the two key secondary efficacy endpoints. MCMC will be first applied to augment data into monotonic missing pattern and PROC MI will be used to generate 30 'complete' datasets using the regression method including the following variables in the imputation model: baseline value, treatment group, stratum (vIGA-AD categories [moderate vs severe]), and measurements at each visit up to the end of the analysis period. The seed for PROC MI will be set as the numeric form of the date when the 1st subject in this study is randomized. The imputed post-

baseline measurements will be rounded to the same precision as the observed data before the determination of responder status. Using the CMH model adjusted by stratification factor (vIGA-AD categories [moderate vs severe]), the imputed endpoints will be analyzed using each of the 30 datasets. SAS PROC MIANALYZE will be used to generate the final inferences of the risk difference between treatment groups.

In both Period A and Period B, efficacy assessments after the first dose of rescue or prohibited medication will not be included in the analyses for that period. As a result, after the first dose of rescue or prohibited medication, the subjects will be considered as non-responders in the NRI approach and will be considered as missing in OC and MMRM analyses.

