### **3.2 Secondary Endpoint(s)**

The key secondary endpoints for this study are:

1. The proportion of subjects achieving validated Investigator Global Assessment Scale for Atopic Dermatitis (vIGA-AD) of "0" or "1" (on a 5-point scale) with a reduction from Baseline of  $\geq 2$  points at Week 16.
2. The proportion of subjects achieving a reduction of  $\geq 4$  points in worst pruritus numerical rating scale (NRS) from Baseline to Week 16.

Other secondary endpoints that are not included in the multiplicity testing procedure (see Section 12.0) are listed below and will be evaluated for each of the specified time points:

- Percent change in EASI from Baseline to Week 16, Week 28, and Week 52.
- Proportion of subjects achieving EASI 75 at Week 28 and Week 52.
- Proportion of subjects achieving EASI 50 at Week 16, Week 28, and Week 52.
- Proportion of subjects achieving EASI 90 at Week 16, Week 28, and Week 52.
- Proportion of subjects achieving vIGA-AD of "0" or "1" with a reduction from Baseline of  $\geq 2$  points at Week 28 and Week 52.
- Change in body surface area (BSA) from Baseline to Week 16, Week 28, and Week 52.
- Proportion of subjects achieving 50% improvement in SCORing Atopic Dermatitis (SCORAD 50) at Week 16, Week 28, and Week 52.
- Proportion of subjects achieving SCORAD 75 at Week 16, Week 28, and Week 52.
- Proportion of subjects achieving SCORAD 90 at Week 16, Week 28, and Week 52.
- Proportion of subjects achieving Dermatology Life Quality index (DLQI) of "0" or "1" at Week 16, Week 28, and Week 52.
- Proportion of subjects achieving Children's Dermatology Life Quality index (CDLQI) of "0" or "1" at Week 16, Week 28, and Week 52.
- Proportion of subjects achieving a DLQI improvement of  $\geq 4$  points at Week 16, Week 28, and Week 52 among subjects with a DLQI  $\geq 4$  at Baseline.
- Change in DLQI from Baseline to Week 16, Week 28, and Week 52.
- Change in CDLQI from Baseline to Week 16, Week 28, and Week 52.

- Change in worst pruritus NRS from Baseline to Week 16, Week 28, and Week 52.
- Proportion of subjects achieving a reduction of  $\geq 4$  points in worst pruritus NRS from Baseline to Week 28 and Week 52.

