### **Analysis of Continuous Variables**

The model based mean and standard error will be provided for continuous variables. The Baseline and visit means will also be presented for each treatment group among subjects who have both Baseline and at least one post Baseline visit values. Treatment groups will be compared using MMRM model as described in Section 8.2 with treatment, vIGA-AD categories and the corresponding baseline value in the model. Point estimates and 95% CIs of mean change from baseline within treatment groups, and between each risankizumab treatment group and placebo will be provided.

Unless otherwise specified, any subject who is randomized based on a wrong stratum will be analyzed according to the actual stratum the subject belongs to.

"Baseline" refers to the last non-missing observation before the first administration of study drug or randomization if no study drug is given.

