#### **8.3.3 Primary Efficacy Analysis**

Pairwise comparison of the primary endpoint of EASI 75 will be conducted between each risankizumab group versus the placebo group using the CMH test adjusting for the stratification factor of vIGA-AD categories.

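### The Period A MMRM fits one baseline slope to all visits; if the true slope changes over time, Week 16 standard errors for continuous secondary endpoints could be up to about 10% larger than with a baseline-by-visit term that costs almost nothing.

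*SAP*

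**What the plan says.** SAP 8.2 lists the MMRM terms. It has "categorical fixed effects of treatment, visit and treatment-by-visit interaction", the vIGA-AD stratum, and "the continuous fixed covariates of baseline measurement". On the covariance it says "An unstructured variance covariance matrix will be used". SAP 8.1, under continuous variables, describes the comparison again, "with treatment, vIGA-AD categories and the corresponding baseline value in the model". Neither place has a baseline-by-visit interaction, so as written a single baseline coefficient applies to all Period A visits.

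On the role of the model, SAP 8.2 says: "MMRM will be the primary approach in the analysis of continuous variables in Period A". It therefore produces the Week 16 differences and intervals for percent change in EASI and for changes in BSA, worst pruritus NRS, DLQI and CDLQI. One example from SAP 3.2 is "Change in body surface area (BSA) from Baseline to Week 16, Week 28, and Week 52". That section introduces the list as "Other secondary endpoints that are not included in the multiplicity testing procedure". The primary endpoint does not use the MMRM; it is tested "using the CMH test adjusting for the stratification factor of vIGA-AD categories" (SAP 8.3.3).

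The activity schedule (Protocol Appendix D; Operations Manual 2.1) gives four post-baseline visits in Period A for EASI, BSA and worst pruritus NRS: Weeks 2, 4, 10 and 16. DLQI, CDLQI, POEM and SCORAD are collected after baseline only at Weeks 4 and 16.

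**The concern.** Two weeks after the first dose, a subject's value should still track baseline closely. By Week 16 the link has usually weakened. For an absolute change this means a baseline slope that moves over visits. A model with one slope compromises between visits, and generalised least squares tilts the compromise towards the early visits, where the residual variance is small. Week 16, the visit reported, is then adjusted with a slope that belongs mostly to earlier visits.

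The unstructured covariance does not repair this. It describes the residuals, and the misfit is in the mean. The unexplained part is absorbed as extra Week 16 residual variance, so the interval for each dose against only 31 placebo subjects is wider than the collected data require.

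**Working it through.** **The plan's own figure.** The documents state no precision or power for any MMRM endpoint. Their one design figure is the power for EASI 75: 15% against 51%, 31 against 62 subjects, two-sided 0.025 (SAP 2.4). The pooled rate is (31 × 0.15 + 62 × 0.51)/93 = 0.39. The null standard error is √(0.39 × 0.61 × (1/31 + 1/62)) = 0.1073. The alternative standard error is √(0.15 × 0.85/31 + 0.51 × 0.49/62) = 0.0902. Then z = (0.36 − 2.241 × 0.1073)/0.0902 = 1.32, which gives power of 90.7%. This agrees with the stated figure of more than 90%, and the present point does not touch it.

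**Inputs.** From the documents: 31/62/62 subjects, the model terms above, and four visits. Assumed, because the documents give nothing: baseline SD of 1, follow-up SD of 1 unless noted, and the correlations with baseline shown below. Correlations between adjacent follow-up visits are 0.75 to 0.88.

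**Large-sample calculation.** Let β be the vector of true baseline slopes by visit, F the fitted residual covariance including the misfit, and σ² the true residual variance at Week 16.

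- Common slope: b = (1′F⁻¹β)/(1′F⁻¹1)
- Week 16 variance inflation: 1 + (β₁₆ − b)² × Var(baseline)/σ²

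Slopes are for the value itself. Using change subtracts 1 from every slope and leaves the result the same.

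| Correlation with baseline, Weeks 2/4/10/16 | β₁₆ | b | σ² | Variance ratio | SE ratio |
|---|---|---|---|---|---|
| 0.50 throughout | 0.50 | 0.500 | 0.75 | 1.000 | 1.000 |
| 0.60/0.57/0.53/0.50 | 0.50 | 0.555 | 0.75 | 1.004 | 1.002 |
| 0.70/0.60/0.48/0.40 | 0.40 | 0.599 | 0.84 | 1.047 | 1.023 |
| the same, SD rising from 0.9 to 1.2 | 0.48 | 0.604 | 1.21 | 1.013 | 1.006 |
| 0.80/0.70/0.45/0.30 | 0.30 | 0.732 | 0.91 | 1.205 | 1.098 |

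For the last row: 1 + (0.30 − 0.732)²/0.91 = 1.205, and √1.205 = 1.098. The loss is equivalent to 1 − 1/1.205 = 17% of the sample for that comparison.

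**Simulation.** The planned model was fitted to 400 trials per scenario (REML, unstructured covariance, stratum term), with no dropout and with 15% dropout missing at random. The ratios of model-based standard errors were:

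- equal slopes: 0.999
- mild decay: 1.001 to 1.002
- moderate decay: 1.022 to 1.024
- strong decay: 1.093 to 1.105

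The 0.999 is the price of the extra term when it is not needed, about 0.1%. The mean treatment estimates of the two models differed by at most 0.002 baseline SD in every scenario.

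**By endpoint type, from further simulations under assumed inputs.** For a BSA-like change with correlation falling from 0.85 to 0.58, the Week 16 variance ratio was about 1.04 to 1.07, or 2 to 3% in standard error. With correlation falling from 0.90 to 0.50 it was about 1.20 to 1.21, or 10%. For percent change in EASI it was 0.996 to 0.998, so no gain.

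**Slopes that also differ by arm.** Proportional improvement in BSA makes the baseline slope differ between drug and placebo. In one set of simulations the common-slope model reported a variance 3 to 24% larger than the interaction model, but the true sampling variance was nearly the same (ratio 0.94 to 1.01). The interaction model's reported variance was 3 to 16% below its true variance. A second set gave a true-variance ratio of 1.04 to 1.06.

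**The case against.** A baseline main effect in an MMRM is a legitimate specification, and nothing in the documents shows that slopes differ by visit. That stands: the loss is conditional. It is zero if slopes are equal, and it is also zero if correlations decay while growing variability keeps the slopes level. The 10% figure needs strong decay.

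The endpoints affected are not powered and not in the multiplicity procedure, so no confirmatory conclusion moves. That also stands and limits the weight of the point.

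Where slopes differ by arm as well as by visit, part of the narrower interval is optimism rather than information. This stands too. It reduces the benefit but gives no reason to prefer the common slope.

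A reader might go further and infer bias in favour of the drug if more severe subjects drop out. The documents do not support this. With dropout related to baseline equally in all arms, the slope error cancels in the treatment difference. A check with SD 22, correlations 0.90/0.80/0.65/0.50 and about 17% dropout by Week 16 gave a difference between models of −0.003 BSA points (SE 0.04). A shift (−0.59, SE 0.04) appeared only when dropout was set higher on placebo, and the documents give no dropout rates by arm.

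A reader might also call the extra term free. It is close to free at 155 subjects, but that was not tested for small subsets. CDLQI is completed only by subjects under 16 at baseline (Operations Manual 3.4), and their number is unknown.

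**Conclusion.** The point holds as a minor, conditional refinement. The plan allows the treatment effect and the covariance to vary by visit but holds the baseline slope constant, with no reason given. The Week 16 standard error is 0% larger than necessary with equal slopes, about 0.2 to 3% larger with mild to moderate decay, and up to about 10% larger with strong decay. Absolute changes such as BSA are the plausible candidates; percent change in EASI is essentially unaffected. All of these sizes rest on assumed SDs and correlations, and on slopes that change over visits in a similar way in each arm. Where they do not, the true gain is smaller than the reported interval suggests.

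The point is about precision, not bias. It reaches only the continuous secondary and additional endpoints in Period A. The primary and key secondary tests, their type I error control and the sample size are untouched. The documents do not support reading it as an error in the plan or as a certain loss.

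**What to change.** In SAP 8.2, give the fixed effects as treatment, visit, treatment-by-visit, vIGA-AD category, baseline value and baseline-by-visit, for the continuous Period A endpoints. Mirror this in SAP 8.1. For very small subsets such as CDLQI, the main-effect model may be kept, and the SAP should say so.

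The change is to SAP wording and programming, with no new data. It adds three parameters for endpoints with four post-baseline visits and one for those measured only at Weeks 4 and 16. The cost is about 0.1% in standard error at 155 subjects when slopes are equal. It should be made before the blind is broken for the Week 16 analysis, the point by which Protocol 7.1 requires the SAP to be final.

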## 13.0 Version History

**Table 2. SAP Version History Summary**

Version	Date	Summary
1.0	01 May 2018	Original version
2.0	04 June 2018	Eligibility criterion 10, requesting a minimum weekly average of daily worst pruritus of at least 4 on an NRS, has been added to the Study Protocol Amendment 1. Therefore, the SAP language describing the NRS related endpoints have been updated accordingly to match the protocol requirement.
3.0	14 February 2019	Two additional efficacy endpoints are added to Study Protocol Amendment 2. Therefore, SAP is updated accordingly.
4.0	17 September 2019	Analysis details have been added to the SAP. In addition, actigraphy related endpoints have been removed due to removal of the actigraphy assessment from the protocol.
5.0	14 October 2020	Updated the method of NRI-C as the primary approach for analyzing categorical endpoints with handling missing data due to COVID-19. Also added details of the NRI-NC approach as sensitivity analysis with no special data handling for missing due to COVID-19. Clarified that OC analysis will be used for summary of all efficacy variables in Period B. Updated the number of imputed datasets from PROC MI to 30. Also updated the protocol deviation categories for summary and the area of safety interest categories to be consistent with the current product safety SAP.

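### Period B response rates drop rescued EASI non-responders from the denominator, and the SAP does not settle whether a non-responder analysis is also reported at Weeks 28 and 52

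*SAP*

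**What the plan says.** SAP 8.2 assigns methods by period. For Period A, "The NRI-C will be the primary approach in the analyses of categorical variables in Period A" and "MMRM will be the primary approach in the analysis of continuous variables in Period A". For the second period, "OC analysis will be used for the summaries of long-term efficacy for all variables in Period B". The entry for version 5.0 in SAP Table 2 repeats this: "Clarified that OC analysis will be used for summary of all efficacy variables in Period B".

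Under OC, a subject with no evaluation at a visit is left out at that visit. In addition, "OC will exclude values after a subject prematurely discontinues from study drug". The last paragraph of SAP 8.2 deals with rescue. "In both Period A and Period B, efficacy assessments after the first dose of rescue or prohibited medication" are left out of that period's analyses, and from then on "the subjects will be considered as non-responders in the NRI approach and will be considered as missing in OC and MMRM analyses".

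Protocol 5.4 (Rescue Therapy) opens topical rescue only after the Week 24 assessments. It is open only to subjects below EASI 50 at both the current and the preceding scheduled visit.

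SAP 3.2 lists EASI 50, 75 and 90 at Weeks 28 and 52 among the other secondary endpoints, outside the multiplicity procedure.

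**The concern.** Permitted rescue selects on the outcome being reported. A subject who qualifies is a known EASI non-responder, and OC then removes that subject from the later visits. More rescue gives a smaller denominator with the same numerator, so poorer disease control can look like better long-term response. If the dose groups use rescue unequally, OC can also create a gap between them, in a direction that cannot be known in advance.

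The protocol leans the other way in a related case. Protocol 5.4 classes subjects who take prohibited topical treatment before the Week 24 assessment as treatment failures. Weeks 16 to 24 lie in Period B, where OC would make the same subjects missing.

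The harm would largely disappear if NRI were reported next to OC, because SAP 8.2 counts rescued subjects as non-responders under NRI. The SAP does not say clearly whether that will happen.

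**Working it through.** **Inputs.** From SAP 2.4: 62 subjects per risankizumab arm and 31 on placebo. From SAP 2.3: placebo subjects are re-randomised 1:1 at Week 16, so about 15 per sequence if all continue. The documents give no rescue, discontinuation or response rate for Period B, so there is no planned figure to reproduce. All such rates below are assumptions.

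**Which visits are exposed.** The Week 24 assessment precedes rescue and is kept. Week 28 can lose only subjects rescued after Week 24. Week 52 can lose those rescued after Week 24, 28 or 40.

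**Rescue component, other missing data held fixed.** With x responders among N subjects and r rescued:

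- rate with rescue as non-response = x/N
- OC rate = x/(N−r), which is N/(N−r) times the first rate

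| N | x | r | Rescue as non-response | OC |
|---|---|---|---|---|
| 62 | 25 | 3 | 25/62 = 40% | 25/59 = 42% |
| 62 | 25 | 6 | 40% | 25/56 = 45% |
| 62 | 25 | 12 | 40% | 25/50 = 50% |
| 15 | 6 | 1 | 6/15 = 40% | 6/14 = 43% |
| 15 | 6 | 3 | 40% | 6/12 = 50% |

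**Unequal rescue between doses.** Take 22 of 62 responders (35.5%) in both arms, with 6 rescued in one and 19 in the other. OC gives 22/56 = 39.3% and 22/43 = 51.2%. That is a gap of 11.9 points in favour of the arm with more rescue, although the arms are equal when rescue counts as non-response.

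**Adding discontinuation.** OC also drops values after study-drug discontinuation, which Protocol 5.6 continues to collect. Let p be the response rate with rescue as non-response and leavers counted as they actually respond, r the rescued share, d the discontinued share, and q the response rate among leavers. Then OC = (p − qd)/(1 − r − d). With p = 0.40, r = 0.05 and d = 0.10:

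- q = 1: 0.30/0.85 = 35%
- q = p/(1−r) = 0.421, leavers like other non-rescued subjects: 0.358/0.85 = 42%
- q = 0: 0.40/0.85 = 47%

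OC exceeds p when q < p(r+d)/d = 0.40 × 0.15/0.10 = 0.60. Only the rescue component has a fixed direction.

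**Is NRI also planned for Period B?**

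- *Pointing to OC only:* NRI-C and MMRM are named as primary for Period A, OC is assigned to all Period B variables, and version 5.0 describes this as a clarification.
- *Pointing to NRI or MMRM as well:* the rescue paragraph in SAP 8.2 covers both periods and describes NRI handling. NRI-NC is given no period limit. SAP 8.4.2 assigns NRI to the other binary secondary endpoints and MMRM to the continuous ones, and the list in SAP 3.2 includes Weeks 28 and 52. SAP 8.5 assigns NRI and MMRM at all applicable visits.
- *Confusing both readings:* SAP 8.4.2 words the NRI analysis as a comparison with placebo, but no subject stays on placebo after Week 16. It cites Section 3.3 for a list that is in 3.2. SAP 8.5 cites Section 3.5, the pharmacokinetic section, for endpoints listed in 3.3.
- *Protocol 7.3* applies NRI from the point of rescue, but only for the primary and key secondary endpoints, all at Week 16.

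**The case against.** The strongest reply is that OC only is the natural reading. SAP 8.2 divides methods by period, version 5.0 confirms it, the NRI sentence in 8.4.2 needs a placebo group and so can be read as Period A, and NRI-NC is only the sensitivity version of NRI-C. That reading is plausible. It does not explain the two-period rescue paragraph, the MMRM assignment for continuous secondary endpoints, or 8.5. If it is right, the denominator problem applies in full. If NRI is also meant, the problem is largely answered, but the SAP has to say so.

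Protocol 7.3 could also be read as reaching Period B, because permitted rescue starts only after Week 24 and the same variables are analysed at all visits. That is a fair reading. It adds to the uncertainty, since the sentence names only Week 16 endpoints.

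Three limits stand. First, Period B is descriptive, and OC is a legitimate summary of an extension. Second, OC is inflated relative to counting rescue as non-response. Against a rate that uses data after rescue, OC is too high only if rescued subjects respond less often than the others (with 22 responders and 12 rescued of 62, below 22/50 = 44%). Third, a reader could approximate the NRI rate from OC responder counts and the population counts in SAP 5.0. The SAP plans no rescue counts by visit, however, so the reader could not separate rescue from other missing data.

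NRI-NC has its own bias, because it counts most visits missed through COVID-19 as non-response.

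**Conclusion.** The concern holds. As written, OC removes known EASI 50, 75 and 90 non-responders from the Week 28 and Week 52 denominators, and the SAP leaves open whether any planned table counts them. The factor N/(N−r) follows from the SAP's rules with other missing data held fixed. For an arm of 62 it is 62/59 = 1.05 with 3 rescued, 62/56 = 1.11 with 6 and 62/50 = 1.24 with 12. The rescue numbers are assumptions. Net OC error can go either way once discontinuation is included, and a distortion between doses requires unequal rescue. The Week 16 primary and key secondary results and their error control are untouched. This should be corrected, but it does not threaten the trial's main inference.

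**What to change.** In SAP 8.2, replace the Period B sentence with text to this effect:

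> Binary response endpoints in Period B are reported by NRI-NC, with subjects counted as non-responders after their first rescue or prohibited medication in that period, alongside OC. Denominators, numbers rescued and numbers discontinued are shown by visit and by treatment sequence (150/150, 300/300, placebo/150, placebo/300).

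State also whether NRI-NC uses assessments made after study-drug discontinuation. State whether atopic dermatitis therapy started after discontinuation counts as rescue or prohibited medication for the analysis, since Protocol 5.6 says the rescue criteria no longer apply by then.

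In SAP 8.4.2 and 8.5, limit comparisons with placebo to Period A visits. Reconcile the NRI and MMRM assignments with the Period B OC sentence for binary and continuous endpoints (for example MMRM in Period A and OC in Period B for continuous variables, if that is the intent). Correct the cross-references to Sections 3.2 and 3.3.

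The cost is SAP wording and one extra set of Period B tables. NRI-NC is already defined and needs no new imputation model. Its drawback is that a visit missed through COVID-19 counts as non-response unless the subject responded both before and after it, so the difference between NRI-NC and OC will not reflect rescue alone. No clinical rule changes.
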